#### 1. Aim of study

The aim of this study is to compare the mechanisms, tolerability and efficacy of two high doses of psilocybin versus a 6 week course of a leading antidepressant medication, escitalopram, in major depressive disorder (MDD). This will be a 2-arm, active comparator, double-blind randomised control trial in a total of 60 completing volunteers ('completing' measured by primary outcome measure).

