#### 2. Project outline

#### 2. Main study design

This will be a two-*arm*, active comparator, *double-blind*, *randomized controlled*, betweensubjects, design in up to *60 completing* patients meeting DSM-IV criteria for *major depression* of a moderate to severe degree (17+ on the 21-item Hamilton Depression Rating Scale, HAM-D). The patients will be randomly allocated to two groups. Groups will receive either: 1) two on-site dosing sessions with 25mg p.o. psilocybin, 3 weeks apart, the first dosing session being followed by 6 weeks of daily inert placebo ingestion, 2) two dosing sessions with 1mg psilocybin (to our knowledge, sub-psychoactive), 3 weeks apart, the first dosing session being followed by 6 weeks of daily escitalopram (10 mg for the first 3 weeks then increasing to 20 mg for 3 weeks, in line with prescribing guidelines [79] and similar to previous literature [98]). See Figure 1 for details.

Condition one is the main experimental condition and condition 2 is a control condition. Condition 2 involves 6-weeks of treatment with a gold-standard antidepressant, escitalopram, adding an important comparative efficacy component to this trial. Both groups will receive equal preparation and follow-up before and after the dosing session. The blind is broken after 6 weeks, after which normal treatment ensues.

**Figure 1. Basic design.** Active components are highlighted in red. Please note, the psilocybin 'dosing sessions' are variously called 'dosing days' in what follows

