#### 2.4.1 Managing risks related to withdrawal from antidepressants

PSILODEP RCT – Study Protocol, Version 7, 11/07/2019

Serotonergic antidepressants are known to attenuate the acute psychological effects of psychedelics [8] and thus, we feel it is necessary that patients withdraw from these medications in order to experience the full effects of the 25mg dose of psilocybin. This washout component of the design is consistent with our recent pilot study, as this was done safely and effectively in that trial. Withdrawal symptoms and a worsening of depressive symptoms can occur with antidepressant-withdrawal [9]; thus, we will incorporate a number of contingency measures to reduce associated risks, namely:

1) Patients will be free to leave the study at any point and return to their treatment as usual if they, their mental-health care-giver or the study team feel this is the right course of action.

2) The study blind will be broken at 6-weeks after the initial dosing session (fig 1), enabling patients to return to pre-study treatment/s if they so choose.

3) Study clinicians will offer telephone contact to patients during the withdrawal period, if this is required.

It is important to note that since recruitment to this trial is not restricted to patients with treatment-resistant depression, potential volunteers may well be unmedicated at the time of study entry. Thus, we can anticipate that challenges relating to withdrawal from medication will be less than in our previous open-label trial in treatment-resistant depression. Even so, antidepressant medication withdrawal was managed safely and effectively in that trial and we foresee that the same will be true in this trial.

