of medications, we will discuss with the patient and their GP or mental health caregiver whether the patient should withdraw from the trial so that previous medications can be resumed or new ones given. There will be ~7 weeks from the first (post-screening) study visit (**visit 2, scan 1**) to the primary end point/blind broken (**visit 7**), after which patients may return to their normal treatments if they so wish.

Patients will be required to make **7 visits** (see fig. 2). Patients will be assessed for up to six months after the initial dosing session; however, the study blind will be broken 6 weeks after the dosing session. Treatment as normal can then take place after the study blind has been broken.

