#### Visit 4 (time since first dosing session = 1 day)

**One day** after dosing, patients will be asked to complete some questionnaires (including a daily version of the QIDS [82]) and will also take part in a structured interview/integration session. Patients will be asked about their experiences the previous day, how they slept, how they have felt today etc. This visit will take approximately 2-3 hours in total.

Interim period (1 week post-treatment): phone call or Skype/Zoom session to check in with patient. Remote assessments of the QIDS also done weekly throughout the trial. Assessments will be cued via email and/or text (using the Psychedelic Survey platform) and completed electronically (on Survey Gizmo), where the study team can access them.

#### Visit 5 (time since first dosing session = 3 weeks): Dosing session 2

The second dosing session will take place exactly as described in Visit 3/Fig 2 above.

Interim period (4, 5 and 6 weeks post-dosing session 1): remote assessments will continue as before, cued via email and/or text (using the Psychedelic Survey platform) and completed electronically (on Survey Gizmo), where the study team can access them. Patients are free to communicate via email with the study team at any point if issues arise. If additional support is needed, each patient will be allowed a maximum of two additional Skype/Zoom sessions with the study team. This limit is in place in order to avoid an imbalance in the amount of support patients receive.

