#### 4.2. Volunteers

#### 4.2.1. Sample size

A baseline versus 5-weeks post-treatment reduction of -9.2 (SD = 5.6) on the QIDS was observed in our recent pilot study. To inform what can be expected with 1mg psilocybin, we can refer to the recent end-of-life anxiety trial of Griffiths et al. [66] in which the reduction in scores on another standard scale (BDI) seen with the control condition (1-3mg/ 70kg psilocybin) was 50% that of the active condition, i.e. a reduction of 10.7 (22-30mg/70kg, active) versus 5.5 (1-3mg/70kg, control) at 5-weeks post-treatment. If 1mg psilocybin is equally as effective as the 1-3mg/70kg in the Griffiths study, i.e. 50% of the active dose (which is a conservative prediction, given that the difference in doses is greater, and the time since treatment is shorter), we can expect a mean reduction in QIDS scores of 9.2/2 = 4.7 points for

the 1mg condition. If we assume equal variance for both conditions, we would require 20 patients per condition to achieve the desired power of 80%, p < 0.05. We therefore propose to recruit a minimum of 30 patients per condition (60 completers in total for the RCT). These are appropriate numbers for the imaging, given that significant baseline v one-day post-treatment effects are being observed in BOLD resting-state functional connectivity, amygdala activations to emotional faces and CBF with just 15 patients in my recent pilot study (papers in preparation). Significant fMRI findings have been reported with escitalopram in similar paradigms and with similar sample sizes [67]. Equivalent efficacy (primary outcome) is predicted for the escitalopram vs 25mg psilocybin conditions but with different mechanisms of action. For example, we predict greater improvements in wellbeing (WEMWBS) with 25mg psilocybin vs escitalopram at 6-weeks post dosing day 1.

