## 4.2.4 Withdrawal Criteria

- 1. Withdrawal of Consent
- 2. Development of concurrent physical illness that necessitates their removal from the trial
- 3. Deterioration of mental health warranting additional input and support
- 4. Dependency or problematic alcohol or illicit substance use

5. Positive pregnancy test in women of childbearing potential (see section 7.2.2) at any point during study

GPs and all relevant health professionals will be informed of their patient's involvement in the trial. Any misgivings or reservations they have about their patient entering and continuing the trial can be responded to by the study psychiatrist.

On entering the trial, should there be any deterioration in the patient's physical or mental health that may compromise their ability to continue in the trial then we will reach an informed decision, once we have the contacted the relevant health professionals, about whether their continued participation is prudent. This will all be done in discussion with the patient and the extended research team.

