## 12. Randomisation

Patients will be randomly allocated to one of the 2 conditions using a random sequence generator such as can be found online:

(https://www.random.org/sequences/?min=1&max=66&col=3&format=html&rnd=new). The sequence can be initiated and managed by the dispensing pharmacist and schedule 1 license holder (Invicro, previously Imanova). Blinding and labelling will be done in collaboration with the manufacturing pharmacy (e.g. GSTT, Juniper and Fisher pharmaceuticals). An example of a random sequence for 2 conditions is provided below:

Condition 1	Condition 2
2	1
3	4
5	6
8	7
10	9
12	11
13	14
15	16
18	17
19	20
22	21
24	23
25	26
27	28
30	29
32	31
34	33
35	36
38	37
40	39
41	42
43	44
46	45
48	47
50	49
51	52
54	53
56	55
57	58
60	59

**Table 1.** Example of a random sequence by which patients recruited to the trial enter the relevant conditions. This sequence is held by the dispensing pharmacy (at Invicro) who do not disclose the randomisation to the study team until situations where the blind is broken.

Patient numbers will be independently monitored by InForm, the data system used by Imperial's in house Clinical Trials Unit (Imp-CTU). Versions of objective tests will be counterbalanced using the same randomisation code (e.g. to ensure a 50:50 split, versions A and B will alternate, with version A provided first). Invicro will also direct the study team as to what version of tests will be used and they will also keep their own detailed log of which patients enter which condition. The Imp-CTU system uses InForm ITM (Integrated Trial Management) System, a web-based data entry system which builds an Oracle database for each individual clinical trial.

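### The trial is sized in completers and patients may leave when symptoms worsen, but the protocol does not commit to comparing all randomised patients or to collecting QIDS after withdrawal

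*Protocol*

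**What the plan says.** The target appears three times in the protocol, each time in completers:

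- Section 1: "in a total of 60 completing volunteers ('completing' measured by primary outcome measure").
- Section 2, main study design: "design in up to *60 completing* patients meeting DSM-IV criteria".
- Section 4.2.1: "We therefore propose to recruit a minimum of 30 patients per condition (60 completers in total for the RCT").

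These read as a fixed total, a maximum and a minimum. No number to be randomised and no dropout allowance is given.

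Section 10 says the study is powered for a t-test of QIDS-16, baseline against week 6, between the two conditions, and calls this the primary efficacy outcome and endpoint. No other efficacy comparison is described.

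Section 2.6 (Visit 1) allocates patients as soon as eligibility is confirmed. Tapering of existing antidepressants, scanning and dosing come later. Three provisions then allow exit linked to symptoms:

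- Section 2.4.1: "Patients will be free to leave the study at any point and return to their treatment as usual".
- Section 2.5, if symptoms rise markedly during washout, has the team discuss with the patient and their caregiver "whether the patient should withdraw from the trial so that previous medications can be resumed or new ones given".
- Section 4.2.4 lists as a withdrawal criterion "Deterioration of mental health warranting additional input and support".

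For weeks 4 to 6, section 2.6 provides that where more support is needed, "each patient will be allowed a maximum of two additional Skype/Zoom sessions with the study team".

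Sections 2.2.1 and 2.6 collect QIDS weekly, remotely, from enrolment to week 6. The protocol does not say whether this continues after a patient withdraws.

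**The concern.** Completing is judged by the primary outcome, so it is known only after randomisation. Patients who deteriorate have three routes out of the trial, and a t-test on change to week 6 cannot use anyone without a week-6 value. If the arms lose different fractions of their worst responders, the remaining groups no longer differ by chance and treatment alone. The arm that loses more of its worst responders then looks better than it is.

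Unequal loss is plausible from the protocol's own text. Section 1.1 expects different side-effect profiles. Section 2.1.2 foresees patients who do not tolerate the higher capsule dose and ask to withdraw. Section 2.6 (Visit 3) describes drug effects as felt at 25 mg only, so some patients may guess their allocation and leave for usual treatment.

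Data not requested after a patient stops cannot be recovered later by any analysis plan. The number to be randomised and follow-up after withdrawal are therefore matters for the protocol itself.

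**Working it through.** **Inputs.** Pilot change in QIDS 9.2 points, SD 5.6 (section 4.2.1). The control change is written as 9.2/2 = 4.7, whereas 9.2/2 is 4.6. The planned difference is therefore 9.2 − 4.7 = 4.5 or 9.2 − 4.6 = 4.6. Stated requirement: 20 per condition for 80% power at p < 0.05, sidedness not given. The protocol states no dropout rate, so every rate below is an assumption.

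**The plan's own figure.** n per arm = 2 × SD² × (z_α + z_0.80)² / δ².

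- One-sided 0.05: 2 × 31.36 × (1.645 + 0.842)² / 4.5² = 19.2, so 20; with δ = 4.6, 19. The stated 20 reproduces.
- Two-sided 0.05: 2 × 31.36 × (1.960 + 0.842)² / 4.5² = 24.3, so 25; with δ = 4.6, 24. The stated 20 does not reproduce.

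With 30 completers per arm, two-sided power is 86% to 89%. The present point does not turn on the 20.

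**Bias from loss in one arm.** Suppose there is no true difference, change is normal with SD 5.6, and one arm loses exactly the fraction p with the least improvement. The mean improvement of those remaining rises by

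shift(p) = 5.6 × φ(z_{1−p}) / (1 − p)

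- p = 0.05: 5.6 × 0.1031 / 0.95 = 0.61
- p = 0.10: 5.6 × 0.1755 / 0.90 = 1.09
- p = 0.15: 1.54
- p = 0.20: 1.96

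If the other arm loses nobody, the bias is 0.6 or 1.1 points for p = 5% or 10%. For scale, the standard error of the difference with 30 per arm is 5.6 × √(2/30) = 1.45.

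**Bias from unequal loss in both arms.** The bias is the difference of the two shifts. The type I error is two-sided, from 40,000 simulated trials with 30 completers per arm. The last column treats half of the dropouts as the worst cases and the rest as random, which replaces p by p/2 in the formula.

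| Loss | Bias, all dropouts worst cases | Type I error | Bias, half worst cases |
|---|---|---|---|
| 5% vs 15% | 0.93 | about 11% | 0.52 |
| 5% vs 20% | 1.35 | about 20% | 0.76 |
| 10% vs 20% | 0.87 | about 11% | 0.48 |
| 10% vs 10% | 0 | 5% | 0 |

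With equal 10% loss of the worst cases the difference is unbiased, but each arm's mean improvement is overstated by 1.1 points.

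**Number to randomise.** N = 60 / (1 − d) for dropout d, rounded up: 64 at 5%, 67 at 10%, 71 at 15%, 75 at 20%, 86 at 30%. Section 4.2.1 equates recruiting 30 per condition with 60 completers. As 2 × 30 = 60, that works only with no dropout.

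**Support passages side by side.** Section 2.6 lets a patient who needs more support stay in, with a limited number of extra sessions. Section 4.2.4 lists deterioration that calls for more support as a ground for withdrawal. The triggers overlap in wording, and which passage is applied affects who reaches week 6. They must be reconciled.

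**The case against.** The strongest reply is that the protocol nowhere says dropouts are excluded. It names no analysis set and no missing-data rule, both commonly left to a statistical analysis plan, and that plan is not shown here. Section 10 says what the study is powered for, which describes sizing more than analysis. Recruiting until 60 complete is itself one way to allow for dropout and is compatible with analysing everyone randomised. This stands. A reader might infer that the protocol removes poor responders from the analysis, but the text does not support that. It leaves the possibility open.

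Withdrawal for deterioration is not automatic either. Section 4.2.4 makes it a case-by-case decision after contact with health professionals and discussion with the patient, so sections 2.6 and 4.2.4 may be meant as graded steps. Exits during washout come before dosing and should be similar between arms while the blind holds. Bias in the difference is a risk that needs unequal loss, and nothing in the protocol shows which arm would lose more.

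Section 1.1 also calls the fMRI measure the primary outcome, so equating completing with having a week-6 QIDS is a reading. It changes little, because sections 4.1.1 and 4.1.2 place both endpoints at week 6.

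A reader might also infer from section 12 that the allocation list stops at 60, so that 60 completers could not be reached. The table there is labelled "Example of a random sequence by which patients recruited to the trial enter the relevant conditions", and the generator link in the same section runs to 66. The list is an illustration and sets no limit.

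What the reply does not answer is the missing number to be randomised, the three versions of the target, and the absence of any commitment to collect QIDS after withdrawal. An analysis plan cannot supply data that were never requested.

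**Conclusion.** The point holds as a risk the protocol leaves open. Size is set in completers, the one named comparison needs a week-6 value, and symptom-related exit is possible after randomisation. Nothing commits the trial to comparing all randomised patients or to following those who withdraw.

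The possible bias is up to 0.6 or 1.1 QIDS points if one arm alone loses its worst 5% or 10%, which is roughly 13% or 24% of the planned difference (0.61/4.6 and 1.09/4.5). It is smaller if loss is only partly driven by outcome, and zero if loss is equal. These figures assume normal change scores with SD 5.6 and dropout rates the protocol does not give. They do not show that the comparison will be biased, nor in which direction. The change is worth making because it is cheap and the follow-up data cannot be obtained afterwards.

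**What to change.** - In section 10, make the primary efficacy comparison include all randomised patients as allocated. Use the weekly QIDS already collected in a repeated-measures mixed model, with the between-arm contrast at week 6. Report the completer t-test as a sensitivity analysis.
- In sections 2.6 and 4.2.4, state that QIDS will be requested to week 6 from patients who stop treatment or withdraw, unless they refuse further contact.
- In section 4.2.1, state the number to be randomised with its assumed dropout, for example 67 at 10% or 75 at 20% to reach 60 completers. Bring sections 1, 2 and 4.2.1 to one target in place of a total, a maximum and a minimum.
- Reconcile the overlapping wording on additional support in sections 2.6 and 4.2.4.

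The cost is mainly wording, some follow-up effort after withdrawal, and a slightly more complex model. The remote QIDS system already exists. The mixed model relies on dropout being explained by the scores already observed, and continued collection after withdrawal reduces that reliance.

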## 1.1. Basic study design

The main experimental condition (**condition 1**) in this study will involve two high doses of 25mg psilocybin (per os, p.o.), 3 weeks apart. The first dose will be followed by 6 weeks of daily (inert) placebo capsule ingestion (condition 1, fig. 1). The control condition (**condition 2**) will involve two dosing sessions, also 3 weeks apart, with a presumed inactive dose of

psilocybin (1mg p.o.). The first dose will be followed by 6-weeks of daily escitalopram capsule ingestion (fig. 1).

Thus, there will be a dedicated on-site dosing day for both conditions (named here 'initial dosing session') followed by 6 weeks of daily capsule ingestion at home and a second dosing session 3 weeks after the first. The primary endpoint for assessing efficacy is 6 weeks after the initial dosing session, when the blind will be broken at the final study visit. Unblinded follow-up will occur for a further 6 months to assess safety and any potential enduring effects.

The main purpose of this design is to test the hypothesis that two doses of psilocybin, a design similar to what may be done in future therapy, will show a superior efficacy to escitalopram and crucially, a different *mechanism of action*. Secondarily, we predict that conditions 1 and 2 will show comparable efficacy at 6 weeks but with a different side-effect profile, e.g. we predict that changes in sexual dysfunction will be different across conditions and that psilocybin will act more rapidly to alleviate depressive symptoms.

Regarding the primary outcome, we will use functional magnetic resonance imaging (fMRI) at baseline and six weeks after the initial dosing session to identify how brain activity changes before and after two doses of 25mg psilocybin vs 6 weeks of daily escitalopram.

We predict that fMRI measured amygdala blood oxygen level dependent (BOLD) responses to emotional faces after-versus-before treatment will be greater in condition 1 (psilocybin) than in condition 2 (escitalopram).

This trial promises to significantly advance our knowledge of the safety, efficacy and mechanism of action of psilocybin for MDD by comparing it with a major conventional treatment for depression. The comparison with escitalopram adds an important component to this trial which may ultimately lead to the development of psilocybin as an alternative treatment option for patients with MDD.

#### 1.1 Background of the study

[figure not shown]
This study is designed to test the efficacy of psilocybin as a treatment for major depression. The burden of depression is severe and increasing. Preventing relapse is a major challenge in depression; first line medications and psychotherapy can decrease symptom severity but large numbers of patients fail to respond and/or relapse when these are discontinued. Psilocybin is a naturally occurring compound that is structurally similar to the endogenous neurotransmitter serotonin. Psilocybin had a brief history of use in psychotherapy in the 1960s but this was cut short before its efficacy could be properly assessed. In recent years, a growing number of studies, including several of our own, have shown that psilocybin can be safely administered to human subjects and there are now consistent reports of persistent improvements in depressive symptoms in depressed patients and other patient groups after just one or two exposures to psilocybin [1; 2; 3; 4; 5]. Our recent open-label feasibility study [1] has provided further preliminary support for the safety and efficacy of psilocybin for treatment-resistant depression, however the data remains inconclusive because of the lack of a control condition. It remains possible that psychological expectations and/or the concomitant psychological support the patients received played a significant role in determining outcomes. It is now important therefore that psilocybin be tested against an appropriate control condition and this is what we propose here.

